6.2 Dispensing

It is the responsibility of the Investigator or his designee to ensure that study product is only provided to study participants. The specific serving size for each product will be provided to each subject.

7. Ethical Issues

7.1 Informed Consent

The investigator will be responsible for submission of the study to the Western Institutional Research Board. Prior to submission of the application, the sponsor will be given the opportunity to review the application. Submission of the application will only take place if both parties agree. The Western Institutional Review Board® meets all requirements of the US Food and Drug Administration (FDA), the Department of Health and Human Services (DHHS), the Canadian Health Protection Branch (HPB), Canadian Institutes for Health Research (CIHR) and the European Community Guidelines. Participants will not be enrolled into the study until they have had the study procedures explained to them, had a chance to ask questions, and given their voluntary consent by signing the consent form. Participants who do not understand English will not be enrolled.

7.2 Confidentiality

Information from the studies may be submitted to the sponsor for its use, and may be sent to the Canadian Therapeutic Products Directorate (TPD) and to the U.S. Food and Drug Administration (FDA), Department of Health and Human Services and the Western International Review Board® (WIRB®). Because of the need to release information to these parties, absolute confidentiality cannot be guaranteed. The results of this research study may be presented at meetings or in publications; however, subject identity will not be disclosed in those presentations.

7.3. Participant Withdrawal Criteria

The Investigator may elect to withdraw the participant from the study or the participant may withdraw from the study at any time. Reasons for withdrawing include, but are not limited to:

- Study product never consumed
- Participant was lost to follow-up
- Participant did not follow study procedures
- Participant elected to withdraw from the study for any reason
- Investigator elected to remove participant from the study for any reason
- Subject takes longer than the specified time to complete the study

In the case of premature withdrawal, all planned assessments for the end of the study visit will be completed. The subject's CRF will be completed including the final assessment. The date and main reason for the premature withdrawal will be clearly documented in the subject's file and written down on the CRF

7.4 Adverse Event Reporting

An adverse event is any symptom, injury, illness, or medical/surgical procedure whether planned or not or whether associated with the study foods or not. Adverse events will be assessed at each visit and recorded in the Case Report Forms. Adverse events will be evaluated for duration, severity, seriousness, and causal relationship to the food items provided in the study by the study physician who will decide if any action is required and provide referral, treatment, and/or follow-up as appropriate until resolved, judged to no longer be clinically significant, or if a chronic condition, until fully characterized. Research staff will record the final outcome and resolution date of the event wherever possible. The action taken and the outcome will be recorded in the Case Report Form.

- It is anticipated that participants enrolled in the study will be clinically managed without the need to add medications or to change the dosage(s) assigned to their current medications. In the event that additional medication is required, or an increase in their medication dosage is warranted, these changes will be recorded as adverse events.
- Investigators are required to report adverse events that fit the following criteria within 10 working days of the time the investigator becomes aware of them:
 - Event is Unexpected (in terms of nature, severity, or frequency) given (a) the research procedures that are described in the protocol-related documents, such as the IRB-approved research protocol and informed consent document, or the Investigator Brochure; and (b) the characteristics of the subject population being studied.
 - Related or possibly related to participation in the research (possibly related means there is a reasonable possibility that the incident, experience, or outcome may have been caused by the procedures involved in the research); and
 - Suggests that the research places subjects or others at a greater risk of harm (including physical, psychological, economic, or social harm) than was previously known or recognized.

If the adverse event is clearly not related to the study drug, device, procedures, or washout process, it would not represent a risk to other subjects in the research or a “problem” for the study and, therefore, does not have to be reported to WIRB.

The Principal Investigator, [name], will be informed within 48 hrs of the nature of the reportable AE and the treatment allocation of the participant in whom it occurred by sending a copy of the AE report via email ([contact]).

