3.4 Withdrawal Criteria

- Withdrawal of consent for any reason
- During the course of the study, the development of an injury or illness or initiation of use of a medication which, in the opinion of [name], makes the subject's continued participation dangerous to the subject or to others, or which may affect the results.
- Failure to follow GI Labs safety guidelines
- Repeated failure to attend at scheduled visits
- Repeated failure to follow the protocol

4. Study Design and Procedures

The study is double-blind with a randomized, cross-over design.

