Visit 2-3: Eligible subjects will be randomized using an online randomization calculator. Eligible subjects will be studied on 2 separate days over a period of 4 weeks or less. Prior to each test meal they will be provided with enough cookies to consume 3 times/day over 3 days and instructed to start consuming these 3 days before their visit. They will also be provided with a calorie appropriate, standard dinner to be consumed on the evening before their test meal. The interval between successive tests will be no less than 6 days and no more than 4 weeks. On each test day, participants will come to GI Labs in the morning after a 10-12h overnight fast (except for water). Participants will be asked to maintain stable dietary and activity habits throughout their participation and refrain from drinking alcohol and from unusual levels of food intake or physical activity for 24h before each test. Before the start of the test meal, subjects will be asked whether they consumed the provided cookies over the last 3 days as instructed and the standard dinner the evening before. Subjects will be asked to complete a 3d record of supplement consumption and whether they consumed the standard evening meal, in addition to a 3d symptom diary before each test visit. If any subject is not feeling well or has not complied with the preceding experimental conditions, the test will not be carried out and will be rescheduled for another day. On each test day, two fasting fingerprick blood samples will be collected at -5min and 0min. Each sample will consist of 2 vials, one for glucose analysis and one for insulin analysis (4—8 drops of blood each). Questionnaires to record satiety and GI symptoms will be administered. Participants will then be given the test food together with 250ml of water and instructed to consume this over 15minutes. Additional blood samples will be collected 15, 30, 45, 60, 90 and 120min after the start of the test meal. Satiety Questionnaires will be administered at the same time intervals. GI symptom questionnaires will be filled out at 2h in addition to fasting.

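### The trial is declared double-blind, yet every reportable adverse event sends the principal investigator the participant's treatment allocation, with no condition of need and no code-break step

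*Combined protocol and SAP*

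**What the plan says.** Section 4 states: "The study is double-blind with a randomized, cross-over design". The title and the design entry of the synopsis also call the trial double-blind.

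Section 7.4 defines a restricted class of reportable events. An event must be unexpected ("Event is Unexpected (in terms of nature, severity, or frequency) given (a) the research procedures", and so on), related or possibly related to participation, and suggestive of greater risk than previously recognised. Such events are to be reported within 10 working days of the investigator becoming aware of them. The section then says that the principal investigator will be told, within 48 hours, "the nature of the reportable AE and the treatment allocation of the participant in whom it occurred", and that this is done "by sending a copy of the AE report via email".

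Section 6.1 has blinding in its heading but covers only label content and intake logs. Section 4.7 says that an online calculator is used and that orders are assigned by attendance at the first visit. Neither section says who is blinded, who holds the allocation list, or how and on whose authority the code may be broken.

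**The concern.** A double-blind trial normally keeps allocation from investigators unless there is a reason to release it, and records each release. Here release is the routine content of a notice. That breaks the blind for the participant concerned whenever the rule applies, whether or not anyone needs the information.

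What is at stake is the impartiality of decisions taken afterwards by people who have seen the report. Three kinds are open in principle: discretionary withdrawal, the judgement that a participant is fit and compliant enough to be tested, and later causality assessments. Adverse events and gastrointestinal symptoms are listed among the study's outcomes (section 2.2), so safety judgements are part of what the trial reports.

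**Working it through.** No arithmetic settles this, and the plan gives no figure to reproduce. The check sets the provisions side by side.

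1. **Is the disclosure conditional?** No. The only filter in section 7.4 is that the event is reportable. Nothing ties release of the allocation to a need for it or to an emergency.

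2. **Is there a code-break procedure elsewhere?** No. Sections 4.7, 6.1, 6.2 and 7.1 to 7.7 name no code holder, no authorisation and no record of unblinding. The only code mentioned for samples is the test meal code on blood tubes (section 4.10), and its key holder is not stated.

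3. **How much does one notice reveal?** Section 4.3 lists two foods, and each participant has two test visits. Section 4.7 randomises the order. If allocation means the order, it states both periods. If it means the food being taken at the time of the event, the other period follows by elimination. Either way, both of that participant's visits are unblinded.

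4. **Who sees it?** The principal investigator, and anyone who writes or handles the report, because the allocation travels with the copy.

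5. **Which decisions could follow?**
   - Section 7.3 lists as a reason for withdrawal: "Investigator elected to remove participant from the study for any reason".
   - Section 4.1 says: "If any subject is not feeling well or has not complied with the preceding experimental conditions, the test will not be carried out". The test is then rescheduled.
   - Section 7.4 says: "Adverse events will be evaluated for duration, severity, seriousness, and causal relationship to the food items provided in the study by the study physician".

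   The first two are exposed only so far as staff who see the report make them. The third is exposed only if the study physician also sees it. The documents do not settle these overlaps: section 7.3 says Investigator, section 7.4 says Principal Investigator, and section 4.1 does not say who makes the test-day judgement.

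6. **Does the notice arrive in time to matter?** Section 4.1 says: "The interval between successive tests will be no less than 6 days and no more than 4 weeks". Section 7.4 gives no starting point for the 48 hours. If they run from awareness, an event known on the first test day produces a notice before the second test. If they run from completion of a report that may take 10 working days, the notice can come after a second test held at the minimum interval, or before one held near the maximum. An event first known at or after the second test leaves no test-day decision to influence.

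7. **Which outcomes lie outside its reach?** Glucose is assayed by an analyser (section 4.10), and the notice does not alter that measurement. The notice also tells participants nothing, so it does not directly affect their own satiety and symptom ratings.

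**The case against.** The strongest reply is that this is a wording conflict with little practical effect. The primary endpoint is a laboratory measure. Reportable events are tightly defined, and section 7.5 says that no related events have been reported and names the foreseeable reactions, which in ordinary form would be hard to call unexpected. A participant with a reportable event could already be withdrawn without anyone knowing the allocation, under the illness criterion in section 3.4. All of this stands and limits the weight of the point. It does not remove the contradiction, because the rule breaks the blind each time it applies.

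It can also be said that allocation may mean only a coded product. The text does not say so, and section 4.10 refers to a code where a code is meant. If a code was intended, a short clarification is enough.

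A third reply is that the principal investigator may need the allocation for safety. A documented code-break preserves that access.

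A reader might also infer more than the documents support:
- **That the notice always precedes the second test.** The 48 hours have no stated start, so this holds on one reading only.
- **That a lost participant measures the harm.** Losing a pair costs the same precision after any withdrawal, blinded or not. Nothing shows that knowing the allocation would change the decision.
- **That the chance of a triggering event can be estimated.** The documents give no event rate on which to base one.
- **That the ingredients statement on the label (section 6.1) also breaks the blind.** The documents do not show that the two products carry different statements.

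**Conclusion.** The point holds in a limited form. Section 7.4 contradicts the double-blind declaration by making disclosure of allocation automatic for every reportable event, and no part of the documents supplies a code-break step or a code holder. For each participant affected, both periods are revealed.

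The consequence is conditional. It requires that a reportable event occurs, which may never happen in 15 healthy adults. For withdrawal and rescheduling, it also requires that the notice arrives before the second test and that people who see the report make those decisions. For later causality judgements, it requires that the study physician sees the report. The documents confirm none of these conditions, so the size of any bias cannot be determined. It would be wrong to read this as a finding that the glucose comparison is biased. The change is still worth making, because the contradiction is plain and inexpensive to remove.

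**What to change.** Reconcile section 7.4 with the double-blind declaration. Remove the treatment allocation from the routine notice to the principal investigator and from the AE report itself. Add a short code-break procedure that names who holds the allocation code, says how a release is authorised, and requires a record of when and to whom it was released. The conditions for release are for the investigator and study physician to set.

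The cost is a wording change in section 7.4 and a brief procedure, which could sit in section 6.1. The site would need to confirm who can hold the code. Access to the allocation when it is needed is kept, and no assessment, visit or sample size changes.

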7.5 Risks

No adverse events related to ingestion of the RS4 tested in this study have been reported. However, there may be rare occurrences of study product intolerance, as manifested by gastrointestinal symptoms (such as crampy gas, bloating, or watery stools), eczema, rashes, or other signs of allergy.

7.6 Dispensing

It is the responsibility of the Investigator or his designee to ensure that study product is only provided to study participants.

7.7 Source documents and archiving

All documents relating to the study will be kept by the investigator: the original informed consent form, source documents, copy of the CRF, copy of the accountability of products administered, copy of the WIRB (ethics committee) approval and correspondence with the partner. The investigator will authorize direct access to the source documents during monitoring. As required by Canadian law, documents will be kept by the investigator for at least 25 years after the closure of the study.

8. Study Management

Appendix 1—Fibersym Nutritional Data

TECHNICAL DATA

 [name] • [contact] • www.mgpingredients.com

Fibersym® RW

U.S. Patent No. 5855946

Product Description

Fibersym® RW is a resistant wheat starch that typically delivers greater than 85% (d.b.) Total Dietary Fiber (AOAC Method 991.43). Fibersym® RW has a low water-holding capacity that allows for enhanced crispness and ease in formulating higher levels of inclusion to achieve labeling benefits. Providing a smooth texture, neutral flavor and white color, Fibersym® RW is a nearly invisible source of fiber. Applications include bakery products, pasta and nutritional food products to boost fiber content, snack foods and batter products to enhance crispness, breakfast cereals to increase bowl life and maintain crispness, and nutritional products targeting controlled glucose release.

Property	Typical Value	Test Method
Total Dietary Fiber	85% min. (dry basis)	AOAC 991.43
Appearance	Fine powder	Visual
Color	White to off-white	Visual
Odor	Bland	Sensory
Moisture*	< 12%	AACC 44-15
pH	4.5 – 6.5	25% Solids
Ash	3.0% maximum	AACC 08-03
Protein, % (N x 5.7 As is)	0.5% maximum	AACC 46-30 Combustion

*The moisture content can vary depending on environmental conditions during storage.

Microbiological

Aerobic Plate Count	10,000 cfu/g maximum	AOAC 990.12
Mold and Yeast	200 cfu/g maximum	AOAC 997.02
Escherichia coli	< 10 / g	AOAC 991.14
Salmonella spp.	Negative in 375 grams	AOAC 2003.09

Packaging, Storage, and Shelf Life

Fibersym® RW is packaged in multi-ply Kraft bags with a net weight of 50 lbs. (22.7 kg) or 25 kg (55.1 lbs). Various tote sizes and bulk also available. Typical bulk density (packed) is 48 lbs./cubic ft. (769 g/L). The product should be stored in a cool, dry, and sanitary area to achieve maximum stability. Shelf life is two (2) years from the date of manufacture when stored under these conditions.

Ingredient Labeling Statement

Modified Wheat Starch. (Fibersym® RW is Phosphated distarch phosphate wheat starch with CAS Number 977043-58-5 and INS Number 1413.)

Disclaimer Statement

Total dietary fiber meets the above specification at point of manufacture. Additional processing may affect the fiber content of products containing any resistant starch. Due to the nature of the testing procedure, TDF results may vary between laboratories, and it is crucial to use the temperature of 100°C as specified in the AOAC 991.43 test for best reproducibility. Final fiber content may differ from software-based calculations and it is better determined by testing.

The information and recommendations in this document are based on experience and analysis using standard procedures, and are believed to be accurate and reliable. However, they serve merely as typical guides, and are presented in good faith for the benefit of customers. No guarantee, expressed or implied, is made regarding accuracy of the analysis, patent infringement, liabilities, or risks involved from the application of this product.

Issued: 1/23/16
 Revision: 14
 Approved: [name]
 Page 1 of 1

TECHNICAL DATA

 [name] • [contact] • www.mgpingredients.com
FIBERSYM® RW
TYPICAL NUTRITIONAL DATA
Nutrient Information (per 100 grams)

Water	10.5
Calories, insoluble fiber subtracted*	39
Protein (grams) (Nx5.7)	0.15
Total Fat by GC (grams)	0.5
Saturated Fat (grams)	0.2
Monounsaturated Fat (grams)	0.04
cis-cis Polyunsaturated Fat (grams)	0.23
trans Fat (grams)	0.00
Carbohydrates (grams) (by calculation)	87.6
Total Dietary Fiber (grams) (as-is) †	80
Soluble Fiber (1g)	
Insoluble Fiber (79g)	
Ash (grams)	1.25
Calcium (milligrams)	21.8
Iron (milligrams)	<1.0
Sodium (milligrams)	308
Cholesterol (milligrams)	<1.0
Potassium (milligrams)	<3.0

Sugars by HPLC (per 100 grams)

Total Sugar	0.0
Fructose	<0.1
Glucose	<0.1
Sucrose	<0.1
Maltose	<0.1
Lactose	<0.1

Vitamins

Vitamin D, Total	<1 ug/100g
Vitamin A, Retinol	<100 IU/100g
Vitamin C	1.19 mg/100g

This product is not produced with added sugars.

* Per 21 CFR 101.9(c)(1)(i)(c)

† Note: Total Dietary Fiber on a dry basis (db) is typically > 90%, with a minimum db specification of 85%.

The information and recommendations in this document are based on experience and analysis using standard procedures, and are believed to be accurate and reliable. However, they serve merely as typical guides, and are presented in good faith for the benefit of customers. No guarantee, expressed or implied, is made regarding accuracy of the analysis, patent infringement, liabilities, or risks involved from the application of this product.

Issued: 2/8/17
 Revision: 13
 Approved: [name]
 Page 1 of 1

Appendix 2: Physical Comfort Questionnaire

 GI Labs	[name] [contact] www.gilabs.com	SUBJECTIVE PHYSICAL COMFORT
Subject Initials	Subject Number	GIL #

Test Meal _____ Date: _____ Time: _____
 (dd/mm/yyyy)

Symptoms	SEVERITY	Comment
Bloating	Low _____ High	
Belching	Low _____ High	
Nausea	Low _____ High	
Diarrhea	Low _____ High	
Flatulence	Low _____ High	
Other (specify) _____	Low _____ High	

Appendix 3: Satiety Questionnaire

HUNGER

How hungry are you?

Not at all
hungry _____

Extremely
hungry

mm:

FULLNESS

How full are you?

Not at all
full _____

Extremely
full

mm:

DESIRE TO EAT

How strong is your desire to eat?

Not at all _____

Extremely
strong

mm:

PROSPECTIVE FOOD CONSUMPTION

How much food do you think you could eat?

None at
all _____

A large
amount

mm:
